The investigation does involve a route of administration or dosage level or use in a patient population or other factor that significantly increases the risks (or decreases the acceptability of the risks) associated with the use of the drug product.

If Not checked- explain why you believe the risk to subjects is not increased:

Although Estrace is not often prescribed to adolescent girls, there is significant experience with estrogens in this population, generally in the form of oral contraceptive pills. Oral contraceptive pills have been shown safe and effective in adolescent girls, and are commonly used for a number of medical conditions, including hyperandrogenism, as well as for contraception.

X The investigation will be conducted in compliance with the requirements for institutional review set part in part 21CFR56 and with the requirements for informed consent set forth in part 21CFR50 ; and This item must be checked.

X The investigation will be conducted in compliance with the requirements of 21CFR312.7 (Promotion and charging for investigational drugs) This item must be checked.

17. Is this a post-marketing study? No.

Specimens

Specimen Information

IRB-HSR#8588: Assessment of the sensitivity of the hypothalamic GnRH pulse generator to estradiol and progesterone inhibition in normal and hyperandrogenemic adolescent girls (JCM010)

1. Describe the type of specimen to be used:

Blood and urine

2. Will the specimen be obtained BEFORE a subject has signed a consent form?

No.

3. Will you be using viable embryos?

No.

4. Will you be using embryonic stem cells?

No.

5. Will you be using discarded specimens?

No.

Specimen Labeling

1. What information/ HIPAA identifiers will be on the specimen label when it is given to the study team (from clinical labs or other source outside the study team) and/or what information will you put on the specimen.?

Name, medical record #, GCRC protocol #, time (date and clock hour) drawn.

2. If the specimen is given to the study team with information on the label will you delete any of the information on the specimen label?

No.

3. Will any additional data be linked to the specimen by way of a code?

No.

4. Will the analysis on the specimen be done soon (within 24 hours) after it is collected?

Yes and No (see the explanation below)

Samples from the screening exam that are analyzed by UVA clinical labs will be run within 24 hrs.

► IF NO, where will the specimen be stored until analysis is done?

Some samples from the screening exam (FSH, LH, P, prolactin, T4, E₂ and T) will be analyzed and stored by the Research Assay and Analysis core lab

All samples from the inpatient admissions will be analyzed and stored in the Center for Research in Reproduction Ligand Core lab.

Specimen Shipping

1. Do you plan to ship any specimens outside of UVA?No.

Payment

1. Are subjects compensated for being in this study?

Yes.

1a. What is the maximum TOTAL compensation to be given over the duration of the protocol?

\$200 in gift cards.

1b. Explain compensation to be given.

All participants will receive a \$75 Charlottesville Fashion Square Mall gift card per inpatient admission. In addition, participants will receive a \$50 bonus for study completion, also in the form of a gift card. Therefore, a participant who completes the entire study will receive a total of \$200 in gift cards. If a subject only completes one inpatient admission, she will be given a \$75 gift card.

1c. Is payment pro-rated

Yes.

2. Are subjects being reimbursed for travel expenses (receipts /mileage required)?

Yes

► IF YES, explain rate/ amount/ upper limits of reimbursements.

When round trip travel exceeds 100 miles, we will make available travel reimbursement at the proposed Virginia state allowance, not to exceed \$100 per trip. Subjects will be paid by check. Receipts and documentation for mileage will be required to be submitted to the study team.

3. Is money paid from UVa or State funds (including grant funds)?

Yes.

3a. How will the researcher compensate the subjects?

Gift card

3b. Which category/ categories best describes the process of compensation?

Compensation will include an alternative method (petty cash, gift card, other) and tax information will be collected.

► If an alternate method will be used justify why you are unable to issue checks through the UVa Oracle or state system.

This study involves preadolescent and adolescent girls. In past and on-going studies involving the same patient population, we have found that the girls prefer being given gift cards directly at the end of the study to receiving a check in the mail 4-6 weeks later, and this preference is reflected in our ability to recruit subjects. Therefore, we prefer to compensate these subjects with gift cards. We obtain social security numbers for IRS purposes.

Retention Plan

1. Will the outside sponsor provide incentives (in addition to any payment/ reimbursement) for the subjects to remain in the study? No.

Family History/Pedigree

1. What kind of information is being sought? Family history.

(No questionnaire is being used).

2. What identifiers will be recorded with the info (e.g. names, initials, relationship such as mother, father, brother, sister, random number)?

Relationship only.

3. Does any of the information sought potentially expose the subject or a family member to additional risk? No

Bio-statistical Analysis-GCRC

1. What are your plans for the statistical analysis?

Analysis of data will be done by the research assistant using computer statistics programs. Microsoft Excel will be used to for routine data analysis, including comparisons between groups of BMI, baseline hormone levels, etc. Cluster analysis of LH pulsatility will be done using the Cluster7 program. We will consult with a statistician for regression analysis.

The primary outcome variable in this study is the reduction in LH pulse frequency after one week of estradiol and progesterone.

In the original power analysis we estimated that we should aim to study 15 normals and 15 hyperandrogenic girls. Given a power of 0.8 and a type I error rate of 0.05, this would allow us to detect a difference in LH pulse frequency over 12 hours of 1.9 pulses.

After 29 subjects were enrolled, a second power calculation was performed with the aid of [name] of the Department of Health Evaluation Sciences taking into account the preliminary data. This calculation showed that in order to detect a difference in reduction of LH pulse frequency of 1 pulse/11 H between hyperandrogenic subjects and normal controls with a power of 0.8 and type I error rate of 0.05, we will need to enroll 30 hyperandrogenic subjects and 30 normal controls.

2. What is the primary outcome variable upon which a sample size estimate is based?

Reduction in LH pulse frequency

3. Do you have an adequate sample size, or is my sample size larger than necessary?

The sample size of 79 should allow us to detect a difference in reduction of LH pulse frequency of 1 pulse/11 H between hyperandrogenic subjects and normal controls with a power of 0.8 and a type I error rate of 0.05. These calculations take into account the 35% historical dropout/withdrawal rate.

Risk/ Benefit Analysis

1. What are the potential benefits for the participant as well as benefits which may accrue to society in general, as a result of this study?

Although individual subjects are not likely to benefit from participating in this study, it will advance our knowledge of hyperandrogenemia in adolescent girls and the mechanisms of development of polycystic ovary syndrome. If our hypothesis is correct and hyperandrogenic girls are less sensitive to progesterone inhibition of GnRH secretion, subsequent studies could explore treating hyperandrogenemia by administration of progesterone. If hyperandrogenic girls could be treated effectively before or during pubertal maturation, development of clinical PCOS as an adult could be potentially avoided.

2. Analyze the risk-benefit ratio.

This study involves negligible risks, but may provide valuable information about the development of polycystic ovary syndrome (PCOS). Although there are not any direct benefits to the individual study participants, there are significant potential benefits to society as a whole and women with PCOS in particular. The currently available treatments for PCOS in adults are not very effective, and PCOS occurs in 6% of women of childbearing age in this country. We hope that a better understanding of PCOS and its precursors will eventually lead to early recognition and prevention of the disorder as well as more effective treatments. Therefore, potential benefits are great while risks are very small.

3. Do you plan to use MRI with Gadolinium in subjects with a GFR<45, acute kidney injury, history of paraproteinemia such as multiple myeloma, hepatorenal syndrome or liver transplant?No.

Data and Safety Monitoring Plan

1. Definition:

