The PI and co-investigators have extensive experience in studies of the early manifestations and abnormalities of pubertal maturation during research over the past 25 years. Much of this research has involved joint collaboration with colleagues in the Department of Pediatrics, and this continues in the present application with co-investigators in the Dept. of Pediatrics. These individuals are specialists in pediatric endocrinology and are well versed and have expertise in dealing with children of the age ranges included. The group currently has 13 ongoing, IRB-approved studies in the adolescent population, including 12 that involve overnight admissions with frequent blood sampling. Over 100 girls to date have enrolled in overnight studies.

Sponsor Information

This study is supported by the Eunice Kennedy Shriver National Institute of Child Health and Human Development (NIH-NICHD).

Support Source

Is there a support source for this study? No

Sharing of Data/Specimens

Data and specimens collected under an IRB approved protocol are the property of the University of Virginia. You must have “permission” to share data/ specimens outside of UVa other than for a grant application and or publication. This “permission” may come in the form of a contract with the sponsor or a material transfer agreement (MTA) with others. A contract/ MTA is needed to share the data outside of UVa even if the data includes no HIPAA identifiers and no code that could link the data back to a HIPAA identifier.

Do you confirm that no data will be shared outside of UVa, beyond using these data for a grant application and or publication, without a signed contract/MTA approved by the SOM Grants and Contracts office/ OSP or written confirmation that one is not needed? Yes.

Do you confirm that no specimens will be shared outside of UVa without a signed contract/MTA approved by the SOM Grants and Contracts office/ OSP or written confirmation that one is not needed? Yes.

International Research

1. Will this study be done outside the U.S. under the oversight of a UVA PI? No.

Hypothesis to be Tested

Adult women with polycystic ovarian syndrome (PCOS) are relatively resistant to suppression of GnRH/LH pulse frequency by the combined slowing effects of estrogen and progesterone. We propose to test whether adolescent girls with hyperandrogenemia, which is thought to be a precursor to PCOS, are also relatively resistant to LH pulse frequency suppression by estrogen and progesterone.

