- Hemoglobin <11.5 g/dL for non-African American subjects; Hemoglobin < 11.0 g/dL for African American subjects (Subjects will be offered the opportunity to take iron supplementation for 60 days if their hemoglobin is below the above stated guidelines, and will then return for retesting of their hemoglobin. If still below the guidelines, they will be excluded.
- Weight < 31 kg
- History of peanut allergy, deep venous thrombosis, breast cancer, endometrial cancer, or cervical cancer
- On hormonal medications (including oral contraceptive pills) or on medications known to affect the reproductive axis within 3 months of the study

IRB-HSR#8588: Assessment of the sensitivity of the hypothalamic GnRH pulse generator to estradiol and progesterone inhibition in normal and hyperandrogenemic adolescent girls (JCM010)

- Pregnant or breastfeeding
- Participation in a research study within the past 30 days that involved taking a study drug.
- Participation in a research study that involved taking up to or greater than 473 ml's of blood within the past 60 days.
- Cigarette smoking
- History of surgery that required bedrest within the past 30 days
- Family history of hypercoagulability or unexplained thromboembolic disease (not in setting of bedrest, surgery, or malignancy)

3. List any restrictions on use of other drugs or treatments.

Subjects must discontinue all hormonally-active medications at least 3 months prior to the frequent sampling study (and 2 months prior to screening visit) and must not take any other medications known to affect the reproductive axis during the study. There are no dietary requirements for this study.

Study Design: Biomedical

1. Will controls be used?

Yes. Controls (normal healthy volunteers) will be used included in all analyses. Thus far, 28 controls have completed the study. Since this is adequate for our purposes, no additional controls will be enrolled. For the remainder of the study, only girls with hyperandrogenemia will be studies.

► IF YES, explain the kind of controls to be used.

Normal-weight, healthy adolescent girls.

2. What is the study design?

Biomedical

3. Is randomization involved?

No.

4. Does the study involve a placebo?

No.

Recruitment

1. Do you confirm that you are aware of the following?

Yes.

- *Finders fees paid to an individual are not allowed by UVa Policy*

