Follow-up questionnaires and/or phone interviews will be completed by the subjects 3, 6 and 12 months after the study asking about the onset and frequency of menses and changes in hirsutism. During these interviews, we will specifically address whether pre-menarchal girls had a withdrawal bleed following the study, and if so, whether or not they subsequently continued menstruating. Whenever possible we will also see the patients on 2-3 occasions during the 12 months to obtain blood for T, DHEA-S, E₂, and P measurements (depending on cycle stage).

The PI will inform the subjects verbally of all incidental findings that are of clinical significance or are of questionable significance. A follow-up letter describing the finding should be provided to the subject with instructions to either show the letter to their PC or if the subject has no PCP, the subject should be instructed to make an appointment at UVa or at the Free Clinic

2. Does the study involve the administration/ dispensing of a drug? Yes.

► IF YES, where will the subjects be seen for the administration/dispensing of the drug?

Inpatient Unit: *CRU, alternate UVA hospital unit, or off-site hotel.*

3. If a potential subject does not meet the inclusion/ exclusion criteria will you repeat any of the screening procedures/ tests? Yes.

► IF YES, explain.

Patients with an elevated 17-OHP on screening will be referred to their pediatricians for further testing to rule out congenital adrenal hyperplasia. They will only be able to continue with the study if they have documented normal 17-OHP levels following a cosyntropin stimulation test. Additionally if safety labs

are abnormal during screening (e.g., abnormal liver tests, abnormal TSH), subjects will be asked to return once for repeat (confirmatory) labs to exclude lab error. Repeat testing will generally occur within one month of the original screening lab draw. If exclusionary lab values are confirmed on such repeat testing, subjects will be excluded from participation. The exact amount of blood drawn will depend on the labs being repeated, but the total amount of blood drawn will not exceed 5 ml.

4. If clinically meaningful results are obtained during the course of the study, explain how you will notify the participant.

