
 • constipation 	 Occurs frequently,  Occurs infrequently  Occurs rarely  Frequency unknown

 • dark or black stools 	 Occurs frequently,  Occurs infrequently  Occurs rarely  Frequency unknown

Risk associated with EMLA cream (topical lidocaine and prilocaine, used to alleviate pain): The risks of lidocaine and prilocaine in general may include (frequency not defined) hypotension, angioedema, shock, hyperpigmentation, erythema, itching, rash, burning, urticaria, burning, stinging, edema bronchospasm, and hypersensitivity reactions. However, in the case of topical lidocaine/prilocaine use, the non-dermatologic adverse events mentioned above would be extremely unlikely unless large amounts of topical lidocaine/prilocaine were used (allowing significant systemic absorption).

Risk regarding wrist actigraphy: There are no known risks associated with the use of wrist actigraphy.

Risk of not being able to take hormonal medications: The risk of not taking hormonal medications is pregnancy.

2.2 List by bullet format a summary of safety tests/procedures/observations to be performed.

- Sterile technique will be used.
- Before participation in the study, all participants will be required to have a normal hemoglobin (≥ 11.0 g/dl for African American subjects and ≥ 11.5 g/dL for non-African American subjects). Hemoglobin levels will be measured prior to every admission, and the admission will only continue if the hemoglobin level is ≥ 11.0 g/dL for African American subjects or ≥ 11.5 g/dL for non-African American subjects.
- Blood loss will be carefully recorded and limited to a maximum of 7cc/kg (10% of estimated total blood volume) in 8 weeks. A total of 216.5 ml of blood will be drawn during the study (including estimated waste from frequent blood draws). Therefore, girls weighing less than 31 kg will not be able to participate. Iron supplementation (325 mg once or twice a day dependent on weight) will be prescribed to all participants.
- Topical lidocaine and prilocaine (EMLA) cream may be used to lessen pain associated with IV needle insertion.

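### The 473 mL prior-blood exclusion sets no usable cut-off as worded, and as probably intended it does not fit the protocol's own 7 cc/kg in 8 weeks cap

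*Combined protocol and SAP*

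**What the plan says.** Three parts of the combined protocol bear on this.

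- **Inclusion/Exclusion Criteria, item 2.** One exclusion reads "Participation in a research study that involved taking up to or greater than 473" mL of blood, with a 60-day look-back. Girls under 31 kg are excluded separately. Two other exclusions narrow the group concerned: "On hormonal medications (including oral contraceptive pills) or on medications known to affect the reproductive axis within 3 months of the study", and "Participation in a research study within the past 30 days that involved taking a study drug".
- **Data and Safety Monitoring Plan, section 2.2.** Blood loss is "limited to a maximum of 7cc/kg (10% of estimated total blood volume) in 8 weeks". The same bullet says "A total of 216.5 ml of blood will be drawn during the study", estimated waste included, and draws the 31 kg minimum from these two figures. It also prescribes iron to all participants. Another bullet says "Hemoglobin levels will be measured prior to every admission".
- **Biomedical Research, item 3.** When abnormal safety labs are repeated at screening, "the total amount of blood drawn will not exceed 5 ml".

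No section ties the 473 mL figure to body weight. None says whether the 7 cc/kg cap counts blood taken in other studies.

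**The concern.** An exclusion criterion should give staff one answer. This one supports two. The literal answer excludes every girl whose recent research study took blood. The probable answer excludes only girls with 473 mL or more.

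The probable answer is the one that raises a safety question. The protocol's own limit scales with weight, and the study is open to girls from 31 kg. A flat 473 mL threshold would let in a girl whose earlier research blood, added to this study's, exceeds that limit.

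Section 2.2 does not settle the matter. If its cap counts blood from other studies, the eligibility criterion admits girls who must later be stopped, possibly after hormone dosing has begun. If it does not, no volume rule covers the total. Most subjects are minors and are not expected to benefit directly, so the entry rule should agree with the stated safety limit.

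**Working it through.** **Inputs.** Cap: 7 mL/kg in 8 weeks (56 days), given as 10% of blood volume, which implies 70 mL/kg. Study blood: 216.5 mL. Minimum weight: 31 kg. All are in section 2.2. The 473 mL threshold is in the exclusion criteria.

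**The plan's own figure.** Minimum weight = 216.5 / 7 = 30.93 kg, rounded up to 31 kg. This reproduces. It uses this study's blood alone and leaves 31 × 7 − 216.5 = 0.5 mL to spare.

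**Room for other research blood in the same 8 weeks** = 7 × weight − 216.5:

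| Weight (kg) | Cap (mL) | Room (mL) |
|---|---|---|
| 31 | 217 | 0.5 |
| 36 | 252 | 35.5 |
| 45 | 315 | 98.5 |
| 60 | 420 | 203.5 |
| 98.5 | 689.5 | 473 |

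The room reaches 473 mL only at (473 + 216.5) / 7 = 98.5 kg. A prior draw of 473 mL taken alone is within 7 mL/kg only from 473 / 7 = 67.6 kg.

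**A modest assumed case.** Suppose the earlier study was one sampling-only overnight admission on this protocol's schedule (Biomedical Research, item 1, Day 0). Sampling every 10 minutes from 1900 to 0600 gives 67 samples.

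- Low count: 61 × 0.75 + 6 × 2.5 + 3.0 = 63.75 mL.
- High count, with the 2.5 mL samples additional and the 0700 draw included: 68 × 0.75 + 7 × 2.5 + 3.0 = 71.5 mL.
- Weight needed: (216.5 + 63.75) / 7 = 40.0 kg to (216.5 + 71.5) / 7 = 41.1 kg, before any waste in the earlier study.

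A girl between 31 kg and about 40 kg would exceed the cap with a prior volume of roughly one seventh of 473 mL.

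**Timing.** The second admission begins about 8 days after the first. An earlier draw therefore shares one 8-week window with both admissions only if it falls within 56 − 8 = 48 days before the first. Recruitment, item 7 puts the main study generally 1 to 2 months after screening.

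- Gap of 30 days: the earlier draw must fall within 48 − 30 = 18 days before screening.
- Gap of 60 days: 48 − 60 = −12, so no pre-screening draw qualifies. Such a draw is also more than 56 days before the first admission.

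**Repeat screening blood.** If up to 5 mL of repeat draws is not already in the 216.5 mL and falls in the window, the minimum weight is (216.5 + 5) / 7 = 221.5 / 7 = 31.64 kg, slightly above 31 kg.

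**The case against.** The strongest reply is that the protocol is safe as written. Literally, the criterion excludes any girl with recent research blood, and section 2.2 caps the total in physiological terms whatever the entry rule says. Both points have weight. The reading of 473 mL or more is an inference, and every exposure figure above depends on it. The running cap may be meant to count all blood. But the literal reading makes the number pointless, and the 31 kg floor was derived from study blood alone, so the text does not clearly bring earlier blood under the cap.

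A second reply is that other safeguards cover the risk. The drug exclusions remove most recent interventional studies. Hemoglobin is checked before each admission, section 2.3 adds a hematocrit and hemoglobin stopping rule, and iron is given to everyone. These reduce the risk of anemia. They do not add up volumes, and the drug exclusions do not reach sampling-only studies.

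A third reply is that nobody is shown to be affected. Investigators Experience states: "The group currently has 13 ongoing, IRB-approved studies in the adolescent population, including 12 that involve overnight admissions with frequent blood sampling". It does not say how many of these give no drug or share subjects. That stands: the number exposed is unknown.

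A reader might infer that the plan would let a 31 kg girl lose almost a third of her blood volume: 689.5 / 31 = 22.2 mL/kg, or 31.8% at 70 mL/kg. The documents do not support that as an expected case. It needs the inferred reading, a prior draw of almost 473 mL from a small girl, all draws inside one 8-week window, and a running cap that ignores other studies. Nothing in the documents points to an adolescent study drawing that much.

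**Conclusion.** The exclusion is defective as worded. On its probable meaning it is a flat volume at odds with the protocol's weight-based cap for any girl under 98.5 kg when the draws share a window. The useful measure is the room actually left: 0.5 mL at 31 kg, 98.5 mL at 45 kg and 203.5 mL at 60 kg.

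This rests on three assumptions: that 473 mL or more was intended, that the draws fall within the same 8 weeks, and that a cap stated as a share of blood volume should count all research blood.

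Practical exposure is small and cannot be quantified from the documents. It is mainly recent sampling-only studies in lighter girls. It shrinks as the gap from screening to admission lengthens, and for pre-screening draws it is gone at about 60 days. The 60-day look-back is not a fault, nor is the 31 kg floor for a girl with no other research blood and no extra screening draws. This is a minor safety-eligibility correction with no effect on the primary analysis.

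**What to change.** Replace the 473 mL criterion with: total research blood from all studies, this one included, must not exceed 7 mL/kg in any 8-week period. Check and record it before each admission. The check before the first admission should include the blood planned for the second, so that no girl is dosed and then stopped. State in section 2.2 that the 7 cc/kg limit counts blood from other studies.

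Keep the 31 kg floor for girls with no other research blood and no extra screening draws. A girl with repeat screening draws outside the 216.5 mL (up to 5 mL) needs up to about 31.6 kg, or those draws must fall outside the 8-week window.

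A limit on any 8-week period is better than a fixed look-back from the first admission. A fixed look-back would charge the full 216.5 mL against draws taken 49 to 56 days earlier, which share no window with the second admission.

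The cost is a wording change, a short recorded calculation per admission, and the occasional deferral of a light or recently sampled girl.

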Abstract

Adolescent hyperandrogenemia appears to be a precursor to adult polycystic ovary syndrome (PCOS). We have found that adult women with PCOS have a reduced sensitivity to progesterone inhibition of GnRH pulsatility. We propose to examine progesterone inhibition of GnRH pulsatility in normal and hyperandrogenemic adolescent girls to determine whether this may be an underlying cause of hyperandrogenemia, and eventually, PCOS. The results will help us understand the causes of PCOS and may lead to preventative treatment.

Human Participants

Ages 8-18 years

Sex Female

Race All races will be recruited and enrolled.

Subjects- see below

1. Provide target # of subjects (at all sites) needed to complete protocol to obtain statistically significant results.

52

2. Describe expected rate of screen failure/ dropouts/withdrawals from all sites.

The historic dropout/withdrawal rate in JMC010/IRB#8588 procedures is 35%. We anticipate a need to enroll 79 subjects in order to get the complete data on 52 subjects needed to obtain statistically significant results.

3. How many subjects will be enrolled at all sites? 79.

4. How many subjects will sign a consent form under this UVa protocol? 79.

Clinical Data Repository

1. Will you be obtaining data from the UVa Clinical Data Repository (CDR)? No.

Participation of Children

1. Explain why this research topic is relevant to children.

This is a study of the effects of progesterone administration on gonadotropin (LH) dynamics during puberty. It will advance our knowledge of the mechanisms of normal puberty. Moreover, it will provide important foundational data pertinent to our hypotheses regarding the development of polycystic ovary syndrome during adolescence. If our hypotheses are correct, this study could provide critical data implicating a specific mechanism by which hyperandrogenemia can cause abnormal gonadotropin secretion in those who may go on to develop PCOS. This in turn may provide a sound rationale for treatment of hyperandrogenemic girls in adolescence. If hyperandrogenemic girls could be treated effectively during pubertal maturation, development of clinical PCOS as an adult could be potentially avoided.

2. Is the knowledge being sought in this study already available for children or is it currently being acquired through another ongoing study?

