IRB-HSR#8588: Assessment of the sensitivity of the hypothalamic GnRH pulse generator to estradiol and progesterone inhibition in normal and hyperandrogenemic adolescent girls (JCM010)

There is very limited data on the sensitivity of the GnRH pulse generator to suppression by estradiol and progesterone during the early pubertal period. The knowledge being sought is not currently being acquired through another ongoing study.

3. Provide data that is available in adults in order that the IRB may judge the potential risk in children. If there is no adult data available, provide reasons why not. If this information is available in a sponsor's protocol, you may reference the section # here and not duplicate the information.

Given that the data sought in this protocol is specific to the peripubertal period of development, there are no similar data in adults. However, very similar studies (frequent blood sampling for LH pulse analysis before and after 7 d of estradiol and progesterone) have been performed by our group in adults without significant adverse effects (Pastor et al. 1998). In addition the 62 adolescent girls who have completed the study thus far in IRB-HSC 8588 have had no adverse outcomes.

4. Is the potential subject population likely to include wards of the state or children who are more at risk for becoming a ward of the state?

Yes.

4a. Is the research in this protocol related to the child's status as a ward of the state? No.

4b. Is the research to be conducted in schools, camps, hospitals, institutions, or similar settings in which the majority of children involved as subjects are not wards? Yes.

4c. Are you aware of the following requirement?

If the consent form contains a signature line for both parents the study team will notify the IRB immediately, if at any time during the course of the research, it becomes known that a potential subject is a ward of the state or that a child already enrolled in this protocol becomes a ward of the state. Yes.

Inclusion/Exclusion Criteria

1. List the criteria for inclusion

- Girls ages 8 to 18
- Hyperandrogenemic (testosterone level > 0.4 ng/mL and/or hirsutism)
- Normal screening labs (with exception of the expected hormonal abnormalities inherent in hyperandrogenemia)

2. List the criteria for exclusion

- Abnormal screening labs (with exception of the expected hormonal abnormalities inherent in hyperandrogenemia)
- Congenital adrenal hyperplasia.

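### The power of 0.8 stated for 79 enrolled and 52 completers is not reconciled with the 30 + 30 requirement given for the same difference, power and type I error

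*Combined protocol and SAP*

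**What the plan says.** The protocol's sample-size statements are in four places.

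- **Bio-statistical Analysis-GCRC, item 1.** The second power calculation, made after 29 subjects were enrolled, is for a between-group difference in LH pulse frequency reduction of 1 pulse/11 h at power 0.8 and type I error 0.05. It concludes that "we will need to enroll 30 hyperandrogenic subjects and 30 normal controls".
- **Bio-statistical Analysis-GCRC, item 3.** Asked whether the sample size is adequate, the plan answers: "The sample size of 79 should allow us to detect a difference in reduction of LH pulse frequency of 1 pulse/11 H". Power and type I error are again 0.8 and 0.05, and "These calculations take into account the 35% historical dropout/withdrawal rate".
- **Human Participants, Subjects items 1 to 4.** The target is 52: "We anticipate a need to enroll 79 subjects in order to get the complete data on 52 subjects needed to obtain statistically significant results". The consent count is the same as the enrolment count: "How many subjects will sign a consent form under this UVa protocol? 79".
- **Study Design: Biomedical, item 1.** On controls: "Thus far, 28 controls have completed the study. Since this is adequate for our purposes, no additional controls will be enrolled". And then: "For the remainder of the study, only girls with hyperandrogenemia will be studies".

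Participation of Children, item 3, also mentions "the 62 adolescent girls who have completed the study thus far in IRB-HSC 8588".

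**The concern.** Items 1 and 3 use the same difference, power and type I error, yet one leads to 60 girls and the other to 52 completers out of 79. Nothing connects them. No SD, test or sidedness is given, and 52 is not derived. The 52, 62 and 79 are not split by group. Item 1 speaks of enrolling 30 + 30 without saying whether that is before or after loss. Controls were closed at 28, below the 30 in item 1, and the calculation was not redone for unequal groups. If 52 and 62 are both totals, the completers to date already exceed the number said to be needed, while hyperandrogenemic girls are still to be studied.

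Item 3 is the protocol's direct answer on sample-size adequacy. As it stands, a reader cannot tell how many hyperandrogenemic completers are needed against 28 controls, or whether that number has been reached. Nor can a null result be set against a known detectable difference.

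**Working it through.** **Inputs from the protocol.** Difference Δ = 1 pulse/11 h; power 0.8; α = 0.05; 30 + 30 (item 1); 79 enrolled, 52 completers, 35% loss (Human Participants); 28 controls, closed (Study Design).

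**Assumptions, because the protocol gives none.** Two-sided unadjusted two-sample t-test with equal SDs. The SD is the one that makes item 1 true. The earlier 15 + 15 calculation concerns a different difference and a 12-hour window, and is not used.

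**Step 1: the loss step.** 79 × 0.65 = 51.4, and 52 / 0.65 = 80. So 79 and 52 agree to within one girl. By contrast, 60 completers would need 60 / 0.65 = 92.3, or 93 enrolled.

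**Step 2: the SD implied by item 1.** Power is P(|T| > t(0.975, n₁+n₂−2)), where T is noncentral t with λ = Δ / [SD × √(1/n₁ + 1/n₂)]. Setting power to 0.8 at 30 v 30 gives a standardised difference of 0.7356, so SD = 1 / 0.7356 = 1.359. This recovers item 1 by construction: λ = 1 / (1.359 × 0.2582) = 2.85, power 0.80.

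**Step 3: 52 as the total of completers.** With 28 controls, 52 − 28 = 24 hyperandrogenemic girls. √(1/28 + 1/24) = 0.2782, so λ = 1 / (1.359 × 0.2782) = 2.645 and power = 0.737. The difference detectable at power 0.8 is 1.08 pulses/11 h.

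Sensitivity of that figure:
- Normal approximation (implied SD 1.382): 0.739.
- One-sided throughout: 0.745.
- If 30 was rounded up from 29, 28, 27 or 26 per arm: 0.752, 0.767, 0.782 or 0.798.

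**Step 4: 52 as hyperandrogenemic girls only.** For 28 v 52, √(1/28 + 1/52) = 0.2344, so λ = 1 / (1.359 × 0.2344) = 3.14 and power = 0.873.

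**Step 5: 30 + 30 as enrolled, before 35% loss.** 60 × 0.65 = 39 completers. Power 0.8 at 20 v 19 implies SD = 1.085. Then 28 v 24 gives λ = 1 / (1.085 × 0.2782) = 3.31 and power = 0.901; 28 v 52 gives 0.973.

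**Step 6: hyperandrogenemic completers needed against 28 controls for power 0.8.**
- 30 + 30 evaluable: 33 (power 0.804), or 25 to 33 over the rounding range in Step 3.
- 30 + 30 enrolled before 35% loss: 15 (power 0.803).

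| Reading of 30 + 30 | Completers | Power at 1 pulse/11 h |
|---|---|---|
| Evaluable | 28 v 24 | 0.74 (to 0.80 with rounding) |
| Evaluable | 28 v 52 | 0.87 |
| Enrolled, 35% loss | 28 v 24 | 0.90 |
| Enrolled, 35% loss | 28 v 52 | 0.97 |

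**The case against.** The strongest reply is that only one family of readings falls below 0.8. The others meet or exceed it, and a plan that claims 0.8 is not wrong because it delivers 0.87 or 0.90. Item 1 also speaks of enrolling, which favours the more comfortable reading. There is even a route from 60 to 52: if the 60 allowed for a loss of 1 − 52/60 = 13%, it would leave 52 completers. The implied SD would then be about 1.26, and 28 v 24 would give 0.798. Updating the loss to 35% then gives 80 enrolled, close to 79. Finally, item 1 foresees regression with a statistician's help, so an unadjusted t-test may not be the intended analysis.

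Most of this stands as a limit on the conclusion. It does not supply the missing link, because the protocol states neither a 13% loss nor an SD, and the only loss rate it gives is 35%.

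Two stronger inferences should be resisted.

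- A reader might say that the protocol leaves the stage of these counts undefined. It does not: 52 and 62 are completers, 79 is enrolled or consenting, and 60 is described as enrolment and split 30 + 30. What is missing is the group split of 52, 62 and 79, and how the 60 relates to loss.
- A reader might divide 62 by 0.65, get about 95, and say that the limit of 79 has been breached. That applies a planning rate to an observed count whose group make-up is unknown. The progesterone Drug Information also gives both 15 and at least 62 for adolescent girls treated, so counts may have been updated at different dates.

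**Conclusion.** The power of 0.8 for 79 enrolled and 52 completers is unsupported and not reconciled with item 1. With 30 per arm taken at face value as evaluable girls, a total of 52 (28 v 24) gives about 0.74, some 6 points short, with a detectable difference of about 1.08 rather than 1 pulse/11 h. The shortfall shrinks to nothing if 30 was rounded up from 26. It becomes a surplus if 52 excludes controls (about 0.87) or if 30 + 30 was before 35% loss (about 0.90).

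It would be tempting to conclude that the study is underpowered. The documents do not support that: the direction of the gap depends on which reading is meant. If the 62 completers include the 28 controls, which the protocol does not say, then 62 − 28 = 34 hyperandrogenemic girls would give about 0.81.

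All these figures rest on a two-sided unadjusted t-test with equal SDs and on an SD back-calculated from item 1. Confidence is medium. The point should be fixed because a sample-size claim that the trial relies on cannot be checked.

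**What to change.** Change the text in Human Participants and Bio-statistical Analysis-GCRC; no added subjects are needed.

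1. State the SD, test and sidedness used in the second power calculation, and whether 30 + 30 is before or after loss.
2. Give enrolled and completed counts separately for controls and hyperandrogenemic girls, and say which group or groups 52, 62, 79 and the 35% cover.
3. With controls fixed at 28, replace the 52/79 and 0.8 statement with the required number of hyperandrogenemic completers and the power or detectable difference that follows from those inputs.

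As a check, not as replacement text: that number is about 33 if 30 + 30 are evaluable with the implied SD, and about 15 if they are enrolled before 35% loss.

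The cost is wording only, with no change to the analysis or type I error. The stated power may become slightly less favourable.
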